Similar to PFS, Kaplan-Meier analyses will be performed for TTF and TSF.

Objective Response Rate (ORR)

ORR is defined as the percentage of patients with confirmed complete response (CR) or confirmed partial response (PR) according to RECIST V1.1, relative to all patients who have baseline measurable disease. Confirmed responses are those that persist on repeat imaging study \geq 4 weeks after initial documentation of response.

Patients who die, progress, or drop out for any reason prior to reaching a CR or PR will be counted as non-responders in the assessment of ORR. A patient, who initially meets the criteria for a PR and then subsequently becomes a confirmed CR, will be assigned a best response of CR.

ORR will be assessed and a 2-sided 95% confidence interval will be provided using the Clopper-Pearson formula.

Overall Survival (OS)

OS is defined as the date from first SU dose to the date of death due to any cause. For patients not experiencing the event, their survival times will be censored at the last date they are known to be alive. Similar to PFS, Kaplan-Meier analyses will be performed for OS. The share of patients alive (OS) at 2 year will be measured for the sequence.

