The OS will be defined as the time from date of first SU dose to the date of death of any cause. For patients not experiencing the event, their survival times will be censored at the last date they are known to be alive

Variable name	Definition
OS status	Patient will not be censored for the OS analysis (OS status = 1) in the following cases:
	1) Axitinib discontinued due to Death (cf. CRF page 35)
	2) Death reported in Long term Follow-up (cf. CRF page 36)
	 Death reported on the Study Discontinuation form (cf. CRF page 37)
	In all other cases, patient will be censored for the OS analysis (OS status $= 0$).

OS status and OS time will be calculated as detailed below:

Variable name	Definition					
OS time	The overall survival time will be calculated in months as:					
(months)	 (Date of death reported at time of Axitinib discontinuation - Start date of Sunitinib + 1) / 30.44, if case n°1 described above is reported 					
	 (Date of death reported in Long term Follow-up - Start date of Sunitinib + 1) / 30.44, if case n°2 described above is reported 					
	 (Date of death reported on the Study Discontinuation form - Start date of Sunitinib + 1) / 30.44, if case n°3 described above is reported 					
	Else, the overall survival time will be censored as follows:					
	 (Maximum of {All visits dates reported} - Start date of Sunitinib + 1) / 30.44 					
	Note: Start date of Sunitinib will be the one reported:					
	- at time of Sunitinib initiation visit for patients enrolled at SU initiation (cf. CRF page 11 " Therapy started with Sunitinib in 1st line on ")					
	- at time of Axitinib initiation visit for patients enrolled at AXI initiation (cf. CRF page 26 "Therapy started with Sunitinib in 1st line on")					

- Best Response under Axitinib in 2nd line post Sunitinib

Number and percentages of patients by best response (CR, PR, SD or PD) will be presented.

- Objective Response Rate (ORR) under Axitinib in 2nd line post Sunitinib

ORR is defined as the percentage of patients with complete response (CR) or partial response (PR) according to RECIST from the start to the end of Axitinib treatment (cf. CRF page 29).

Patients who die, progress, or drop out for any reason prior to reaching a CR or PR will be counted as non-responders in the assessment of ORR.

All assessments following an assessment of PD will be excluded from the derivation of ORR.

- Clinical benefice Rate (CBR) under Axitinib in 2nd line post Sunitinib

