The Clinical Benefit Rate (CBR) will be the proportion of patients with a CR, PR or Stable Disease according to RECIST criteria from the start to the end of Axitinib treatment (cf. CRF page 29).

PFIZER CONFIDENTIAL

Page 16 of 41

Patients who die, progress, or drop out for any reason prior to reaching a CR, PR or SD will be counted as non-responders in the assessment of CBR.

All assessments following an assessment of PD will be excluded from the derivation of CBR.

- Objective Response Rate (ORR) under TKI in 2nd line post Sunitinib

ORR is defined as the percentage of patients with complete response (CR) or partial response (PR) as best response under TKI treatment (cf. CRF page 36).

- Clinical benefice Rate (CBR) under TKI in 2nd line post Sunitinib

The Clinical Benefit Rate (CBR) will be the proportion of patients with a CR, PR or Stable Disease as best response under TKI treatment (cf. CRF page 36).

- Objective Response Rate (ORR) under mTOR in 2nd line post Sunitinib

ORR is defined as the percentage of patients with complete response (CR) or partial response (PR) as best response under mTOR treatment (cf. CRF page 36).

- Clinical benefice Rate (CBR) under mTOR in 2nd line post Sunitinib

The Clinical Benefit Rate (CBR) will be the proportion of patients with a CR, PR or Stable Disease as best response under mTOR treatment (cf. CRF page 36).

- Objective Response Rate (ORR) under IO in 2nd line post Sunitinib

ORR is defined as the percentage of patients with complete response (CR) or partial response (PR) as best response under IO treatment (cf. CRF page 36).

- Clinical benefice Rate (CBR) under IO in 2nd line post Sunitinib

The Clinical Benefit Rate (CBR) will be the proportion of patients with a CR, PR or Stable Disease as best response under IO treatment (cf. CRF page 36).

- Objective Response Rate (ORR) for Sunitinib received in 1st line

ORR is defined as the percentage of patients with complete response (CR) or partial response (PR) as best response under Sunitinib treatment (cf. CRF page 12 for patients included at time of Sunitinib initiation, cf. CRF page 26 for patients included at time of Axitinib initiation).

- Clinical benefice Rate (CBR) for Sunitinib received in 1st line

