7 HANDLING OF MISSING VALUES

The majority of data will be collected with a website (except for FKSI-19 and SF-36 questionnaires). In this website, the input of certain data will be obligatory, limiting the number of missing values, particularly for endpoints.

Regarding the descriptive analyses of each variable, it will be based on the available data ("observed-case analysis"), considering missing data as non-informative. The number of missing data will be documented for each analysis.

The analysis of the primary endpoint is a survival analysis which is known to efficiently handle missing data: all patients are included in the analysis and missing data are called right-censored data.

For continuous endpoints (QoL endpoints), a mixed model for repeated measures (MMRM) will be used to analyse longitudinal data. Missing data will not be imputed. However, this analysis will be performed on all patients having a baseline value and at least one post-baseline value. The model will be valid under the assumption of data missing at random (MAR).

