8.1.1 Descriptive Methods

Descriptive analysis of qualitative and ordinal variables will comprise the number and percentage of each category. Percentages will be calculated on the number of all available data, excluding missing data.

Descriptive analysis of quantitative variables will present the mean, the standard deviation (SD) as well as the median, quartile 1, quartile 3, min and max values.

The 95% confidence intervals will be presented for main endpoints. The 'exact' Clopper-Pearson confidence interval will be provided to assess 2-sided 95% confidence interval for main binomial proportions (e.g. ORR rate).

The number of missing values will be reported in the results table for each variable.

8.1.2 Survival Analysis Methods

The survival functions (for PFS, TTF, TSF, OS) will be estimated with the Kaplan-Meier method. The survival function S(t) is the probability that the event (treatment discontinuation, death or progression) does not occur before a specified time.

This method will be applied to derive, survival curves, median event time and a 95% confidence interval for the median survival time (time at which half the analyzed patients have presented the event). Survival curves will give an idea of whether or not the groups are proportional (i.e. the survival functions are approximately parallel). For OS, the share of patients alive at 24 months will also be measured.

The log-rank test of equality across strata will be used to compare survival curves for categorical variables (sub-groups of interest). For continuous variables, a univariate Cox proportional hazard regression will be used.

For analyses of prognostic factors of survival time, multivariate Cox proportional hazard regressions will be performed.

8.1.3 Strategy of Variable Selection in a Cox Model for PFS Analysis

The strategy of selection of variables in multivariate models will consist in: *Step 1: Selection of initial factor*

In a first step, the association between the PFS and each potential factor will be analyzed using

- A Log-Rank test (PROC LIFETEST under SAS 9.4) for categorical factors. Kaplan-Meier curves will also be presented in order to give an idea of whether or not the corresponding groups are proportional (i.e. the survival functions are approximately parallel)
- a univariate Cox proportional hazard regression (PROC PHREG under SAS 9.4) for continuous factors

Only significant factors at the 25% threshold will be retained for the initial model.

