8.2 STATISTICAL ANALYSES

8.2.1 Safety Analyses

Safety analyses will be provided in the safety population.

AEs will be presented overall and by period of treatment (Sunitinib, Axitinib).

They will be displayed in summary tables, by system organ class (SOC) and preferred term (PT).

The tables will present the number of subjects and the rate of occurrence within each period for which the events occurred. The rate of occurrence will be expressed as a percentage of the subjects from the Safety Analysis Set receiving the treatment concerned.

For the number of subjects and the rate of occurrence, the same classification (SOC and / or PT) in the same patient is counted only once.

In a first time, an overview of all AEs will be given overall and by period of treatment (Sunitinib, Axitinib) and will include the description of the number and the percentage of patients with the following criteria:

- At least one AE
- At least one SAE
- At least one non-serious AE
- At least one grade 3 AE
- At least one grade 4 AE
- At least one grade 3/4 AE

Same analysis will be repeated on related AEs only.

Then each of the following categories of AEs will be described by SOC and PT overall and by period of treatment (Sunitinib, Axitinib):

PFIZER CONFIDENTIAL

Page 28 of 41

- All AEs
- Most common AEs (SOC or $PT \ge 10\%$)
- SAEs
- Non-serious AEs
- Grade 3 AEs
- Grade 4 AEs
- Grade 3/4 AEs

Same analysis will be repeated on related AEs only.

Proportion of patients who discontinued the treatment of interest because of AEs will be given with its 2-sided 95% 'exact' Clopper-Pearson confidence interval overall and by period of treatment (Sunitinib, Axitinib).

Treatment duration until discontinuation for AEs will be analyzed using descriptive statistics (mean, standard deviation, median and range) overall and by period of treatment (Sunitinib, Axitinib).

Proportion of patients who died due to any cause will be given with its 2-sided 95% 'exact' Clopper-Pearson confidence interval overall and by period of treatment (Sunitinib, Axitinib). Causes of deaths (tumor-related, other cause) will also be described.

8.2.2 Analyses of Efficacy Endpoints

Efficacy analyses will be provided in the FAS population.

Primary endpoints

PFS under Axitinib in 2nd line post Sunitinib will be described using the Kaplan Meier method in the SU-AXI subgroup:

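### The SAP says how unassessed patients count for axitinib ORR and CBR only; for sunitinib and the other second-line drugs its available-data default can raise the rates

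*SAP*

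**What the plan says.** SAP 6.1.2 defines response rates drug by drug.

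- **Axitinib, ORR:** "Patients who die, progress, or drop out for any reason prior to reaching a CR or PR will be counted as non-responders". Assessments after a PD are also dropped.
- **Axitinib, CBR:** the same two rules, the first ending "prior to reaching a CR, PR or SD will be counted as non-responders in the assessment of CBR".
- **Sunitinib:** "ORR is defined as the percentage of patients with complete response (CR) or partial response (PR) as best response under Sunitinib treatment", with nothing further except the CRF pages to use.
- **Other TKI:** "ORR is defined as the percentage of patients with complete response (CR) or partial response (PR) as best response under TKI treatment". The mTOR and IO entries, and every non-axitinib CBR entry, follow the same pattern.
- **Best response under axitinib:** numbers and percentages for CR, PR, SD and PD, with no row for patients who could not be assessed.

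Two general rules apply where an entry is silent. SAP 8.1.1 states: "Percentages will be calculated on the number of all available data, excluding missing data". SAP 7 bases descriptive analyses on observed cases, "considering missing data as non-informative". SAP 8.2.2 adds "Efficacy analyses will be provided in the FAS population" and plans ORR and CBR for axitinib and for sunitinib. The sunitinib rates are also to be given by MSKCC group at sunitinib initiation.

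Protocol 8.7.1 takes ORR "relative to all patients who have baseline measurable disease" and states the non-responder rule without naming a drug, although the protocol's ORR endpoint is for axitinib only.

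**The concern.** A response can be missing because the patient died, deteriorated or left care before the first scan. Treating such gaps as non-informative removes likely non-responders from the denominator. The axitinib entries guard against this for deaths and dropouts; the other eight entries do not.

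Unassessed patients are to be expected. Visits follow routine care, and the sunitinib follow-up, retrospective sunitinib and long-term follow-up forms all offer NA as a response. For second-line drugs other than axitinib, best response is collected only on the six-monthly long-term form, and the Study Discontinuation form has no response field.

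At stake is whether the response rates in one report share a basis. A reader will set sunitinib and other second-line rates beside the axitinib rates even though no test is planned. There is also an internal problem: if the axitinib best-response table uses available data, its CR and PR percentages can add up to more than the axitinib ORR.

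**Working it through.** **Inputs from the documents.** Planned sizes are in Protocol 8.5: 750 patients in all, 350 with the sunitinib–axitinib sequence, and about 230 with another second-line drug. That last figure reproduces: 525 × 0.68 = 357 with a second line, 357 × 0.35 = 125 on axitinib, 357 − 125 = 232.

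**Inputs not in the documents.** No expected ORR, CBR or unassessed share is given, so there is no figure of the plan's own to reproduce. Assumed: ORR 20% (range 10 to 30%), CBR 60% (range 50 to 70%), m from 0 to 20%.

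**Formula.** Let n patients start the drug, x respond, and a share m have no recorded response.

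- Unassessed counted as non-responders: rate = x / n.
- Unassessed excluded: rate = x / [n(1 − m)].
- Ratio = 1/(1 − m), which is 1 at m = 0 and above 1 otherwise.

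A patient with a recorded PD is in both denominators, so only patients with no recorded response matter.

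**Results.**

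| m | Ratio | ORR 20% becomes | CBR 60% becomes |
|---|---|---|---|
| 0% | 1.00 | 20.0% | 60.0% |
| 5% | 1.05 | 21.1% | 63.2% |
| 10% | 1.11 | 22.2% | 66.7% |
| 20% | 1.25 | 25.0% | 75.0% |

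At m = 20%, an ORR of 10% becomes 12.5% and one of 30% becomes 37.5%; a CBR of 50% becomes 62.5% and one of 70% becomes 87.5%.

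**Against the planned precision (exact 95% intervals, ORR 20%).**

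- Sunitinib, all 750: 150/750 = 20.0% (17.2 to 23.0). With m = 10%, 150/675 = 22.2% (19.1 to 25.6). With m = 20%, 150/600 = 25.0% (21.6 to 28.7), an interval that no longer contains 20%.
- Other second line, 230: 46/230 = 20.0% (15.0 to 25.8). With m = 10%, 46/207 = 22.2% (16.8 to 28.5). With m = 20%, 46/184 = 25.0% (18.9 to 31.9).

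**Axitinib table against axitinib ORR (350 patients, 70 responders).** ORR with unassessed patients as non-responders is 70/350 = 20.0%. On available data, the CR and PR rows would add to 70/315 = 22.2% at m = 10% and 70/280 = 25.0% at m = 20%.

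**The case against.** The strongest reply is that nothing in the non-axitinib entries excludes anyone. They are silent on the denominator, and exclusion is inferred from a sentence in 8.1.1 about categories of qualitative variables. ORR appears later in that section, as a binomial proportion with an exact interval. Efficacy is analysed in the FAS, and the protocol's definition can be read as drug-neutral. This is fair as far as it goes. But the FAS settles who is eligible for analysis, not how a missing response is counted, and the available-data rule is the only one the SAP offers for the gap.

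Other parts of the reply stand:

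- A recorded NA may count as available data and stay in the denominator. The SAP does not say.
- A reader might use the overall survival medians of 12.3 and 16.4 months in Protocol section 6 to argue for a large m, since exponential survival gives 1 − 0.5^(6/12.3) = 29% and 1 − 0.5^(6/16.4) = 22% dead by six months. That does not estimate m. A patient can have a response or a PD recorded and then die, and the medians come from a second-line trial, so they say nothing about first-line sunitinib.
- About 225 of the 750 patients enrol at axitinib start. They cannot have died on sunitinib, so for them only NA or blank responses matter.
- The study is descriptive, and SAP 4.2 plans no test. The protocol's objectives for other second-line drugs are PFS and OS. The available text of SAP 8.2.2 lists ORR and CBR analyses for axitinib and sunitinib only, though its last sentence ends at a colon and a list may be missing there.
- The SAP already requires the number of missing values to be reported, so a careful reader could recompute. The table shells are in separate documents.

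**Conclusion.** The concern holds in a limited form. The SAP states non-responder and post-progression rules for axitinib ORR and CBR only. For sunitinib, other TKI, mTOR and IO, its own defaults would remove patients with no recorded response. Any resulting shift is upward, by 1/(1 − m): nil at m = 0, and at m = 20% 5.0 points on an ORR of 20% and 15.0 points on a CBR of 60%. These sizes rest on assumed rates and an assumed m.

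A reader might infer that every non-axitinib rate is inflated and that the comparison always runs against axitinib. The documents do not support that. It would need m above zero in each group, the exclusion reading in each group, and NA treated as missing. It would also need a comparison that the SAP does not plan; first-line sunitinib and second-line axitinib are not like for like under any denominator.

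What remains is worth correcting because the sunitinib ORR and CBR are definitely planned, with exact intervals and by MSKCC group, and following the SAP as written can bias them in one direction.

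**What to change.** In SAP 6.1.2, set one denominator for every ORR and CBR: all FAS patients with baseline measurable disease who started the drug. Measurable disease is an inclusion criterion and the FAS is limited to eligible patients, so this keeps the protocol's condition and should remove few, if any, patients.

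- Apply the axitinib non-responder and post-progression rules to every drug.
- State that NA and blank responses count as non-response. This also covers patients still on treatment with no assessment, whom the axitinib rule does not name.
- Add a not assessable/missing row, on the same denominator, to each best-response table, so that CR plus PR equals the ORR.
- Report the available-case rate as a sensitivity analysis.

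The cost is SAP wording and table shells; no new data are needed. The reported non-axitinib rates may become slightly less favourable.

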8.2. Setting

The study will enroll patients according to the eligibility criteria in participating countries across Europe. The recruiting centers will be representative of each country involved in terms of care management systems, of size and of practices (at least when performing feasibility).

Any patient who meets the eligibility criteria will be invited to participate in the study with no selection by the investigators. The enrollment visit will be performed at the time of the patients' inclusion, after the patients' acceptation of enrollment in the study.

Data will come from medical records and will be collected in routine clinical practice. The enrollment visit will comprise a first section on patients' eligibility for every patient whatever pool they belong to and a second section depending on the treatment started (SU or AXI) at the inclusion.

For patients enrolled in the study when AXI is started as a 2^{nd} line therapy, a retrospective section will be completed at patients' inclusion, to collect data on SU 1^{st} line treatment.

For patients who start AXI when SU is discontinued during the study, the AXI initiation visit will resume baseline data that need to be updated.

Follow-up will be ensured during visits in the context of usual patients' care management (non-interventional study). No visits will be required by the protocol of the study. As long as the

patients are treated with SU or AXI, every visit to the center will be recorded. In accordance with ESMO guidelines and physicians clinical practice is real life, follow-up visits are approximately expected:

- during SU treatment: every 6 weeks (every cycle) with tumor assessment approximately every 3 months with respect to the clinical practice
- during AXI treatment: every 4 weeks (every cycle) with tumor approximately assessment every 2 months with respect to the clinical practice

[figure not shown]
When patients come off SU treatment (i.e. are not receiving AXI) or come off Axitinib (after receiving the SU-AXI sequence) they will be followed up every 6 months (separate form) for survival until the end of the study.

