6 ENDPOINTS AND COVARIATES

6.1 EFFICACY/EFFECTIVENESS ENDPOINT(S)

6.1.1 Primary Endpoints

- Progression Free Survival (PFS) under Axitinib in 2nd line post Sunitinib

The PFS will be defined as the time from when the patient receives the first dose of AXI to the time of progression or death due to any cause, whichever occurs first.

PFS status and PFS time will be calculated as detailed below:

Variable name	Definition
PFS status	Patient will not be censored for the PFS analysis (PFS status = 1) in the following cases:
	 Tumor Assessment showing PD in at least one Axitinib follow-up visit (cf. CRF page 29)
	 Death within 3 months after treatment discontinuation / last Tumor Assessment. Death could be reported whether on Axitinib discontinuation page (cf. CRF page 35) or on Study Discontinuation visit (cf. CRF page 37)
	In all other cases, patient will be censored for the PFS analysis (PFS status $= 0$).
	Note: the following cases should be discussed at time of DRMs:
	- Patients with a PD not documented through a Tumor Assessment
	- Patients with no regular Tumor Assessments (i.e. not every 3/4 months)
PFS time	The time to disease progression will be calculated in months as:
(months)	 (Date of first Tumor Assessment showing PD in at least one Axitinib follow-up visit - Start date of Axitinib + 1) / 30.44, if case n°1 described above is reported
	 (Date of death - Start date of Axitinib + 1) / 30.44, if case n°2 described above is reported
	Else, the time to disease progression will be censored as follows:

Variable name	Definition
	 (Date of Axitinib discontinuation - Start date of Axitinib + 1) / 30.44 if patient discontinued Axitinib for any reason other than PD
	 (Date of last follow-up visit - Start date of Axitinib + 1) / 30.44 if patient is lost to follow-up or still under Axitinib
	Note; this could be adapted if necessary (to be discussed at time of DRMs)
	Note:
	- Start date of Axitinib will be the one reported at time of Axitinib initiation visit (cf. CRF page 25 "Therapy started with Axitinib in 2nd line on")
	- Axitinib discontinuation date will be the Date of progression/intolerability or death reported at time of Axitinib discontinuation (cf. CRF page 35)

- Progression Free Survival (PFS) for the sequence Sunitinib-Axitinib

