The Clinical Benefit Rate (CBR) will be the proportion of patients with a CR, PR or Stable Disease as best response under Sunitinib treatment (cf. CRF page 12 for patients included at time of Sunitinib initiation, cf. CRF page 26 for patients included at time of Axitinib initiation).

OS status and OS time will be calculated as detailed below:

Variable name	Definition					
OS status	Patient will not be censored for the OS analysis (OS status = 1) in the following cases:					
	1) Death reported in Long term Follow-up (cf. CRF page 36)					
	 Death reported on the Study Discontinuation form (cf. CRF page 37) 					
	In all other cases, patient will be censored for the OS analysis (OS status $= 0$).					
OS time	The overall survival time will be calculated in months as:					
(months)	 (Date of death reported in Long term Follow-up - Start date of Sunitinib + 1) / 30.44, if case n°1 described above is reported 					
	 (Date of death reported on the Study Discontinuation form - Start date of Sunitinib + 1) / 30.44, if case n°2 described above is reported 					
	Else, the overall survival time will be censored as follows:					
	 (Maximum of {All visits dates reported} - Start date of Sunitinib + 1) / 30.44 					
	Note: Start date of Sunitinib will be the one reported :					
	- at time of Sunitinib initiation visit for patients enrolled at SU initiation (cf. CRF page 11 " Therapy started with Sunitinib in 1st line on ")					
	- at time of Axitinib initiation visit for patients enrolled at AXI initiation (cf. CRF page 26 "Therapy started with Sunitinib in 1st line on")					

- Progression Free Survival (PFS) for Sunitinib received in 1st line

PFS status and PFS time will be calculated as detailed below:

Patients included at time of Sunitinib initiation (i.e. prospective group)

Variable name	Definition
PFS status	Patient will not be censored for the PFS analysis (PFS status = 1) in the following cases:
	 Tumor Assessment showing PD in at least one Sunitinib follow- up visit (cf. CRF page 12)

Variable name	Definition					
	 2) Death within 3 months after treatment discontinuation / last Tumor Assessment. Death could be reported whether on Sunitinib discontinuation page (cf. CRF page 17) or on Study Discontinuation visit (cf. CRF page 37) 					
	In all other cases, patient will be censored for the PFS analysis (PFS status $= 0$).					
	Note: the following cases should be discussed at time of DRMs:					

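### The SAP takes death from different CRF forms for different endpoints, so a death recorded only on an unlisted form would be censored in PFS or in the second OS table

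*SAP*

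**What the plan says.** **Definitions.** For OS, SAP 6.1.2 states: "The OS will be defined as the time from date of first SU dose to the date of death of any cause". PFS likewise ends at progression or death from any cause (SAP 6.1.1; protocol 8.1.1, Study endpoints). The SAP's PFS tables then count a death only if it falls within 3 months of the end of treatment or of the last tumour assessment.

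**Where death is looked for.**
- *Primary PFS, axitinib and SU-AXI sequence (SAP 6.1.1):* "Death could be reported whether on Axitinib discontinuation page (cf. CRF page 35) or on Study Discontinuation visit (cf. CRF page 37". First-line sunitinib PFS in the prospective group (6.1.2) has the same sentence with the sunitinib discontinuation page, 17, in place of 35.
- *OS for the SU-AXI sequence (6.1.2):* the list opens with "Axitinib discontinued due to Death (cf. CRF page 35" and adds pages 36 and 37.
- *Second OS table (6.1.2, between first-line sunitinib clinical benefit rate and first-line sunitinib PFS):* "Death reported in Long term Follow-up (cf. CRF page 36" and "Death reported on the Study Discontinuation form (cf. CRF page 37", then "In all other cases, patient will be censored for the OS analysis". Its note on the sunitinib start date also covers patients whose date is taken "at time of Axitinib initiation visit for patients enrolled at AXI initiation".

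**Where death is recorded.** Protocol Annex 1 has a dated death field on the sunitinib and axitinib follow-up visit forms (3.2, 4.2), the long-term follow-up form (5) and the study discontinuation form (6). The adverse event form in Annex 2 also has a date of death. Once patients are off sunitinib without axitinib, or off axitinib, "they will be followed up every 6 months (separate form) for survival until the end of the study" (protocol 8.2).

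**The concern.** Death is a single fact about a patient, and its status and date should not depend on the endpoint being programmed. Here they can. A PFS programmer working from the SAP would look at pages 35 and 37 and pass over the form used for survival follow-up once treatment has stopped. A programmer of the second OS table would pass over the pages on which a death during sunitinib or axitinib is entered.

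A death missed in this way is treated as censoring. The patient leaves the risk set because of the event, so the censoring is informative. Two primary endpoints (axitinib PFS and SU-AXI PFS) are exposed, as is first-line sunitinib PFS. First-line sunitinib OS is exposed too, if that is what the second OS table serves.

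**Working it through.** **Step 1. Source lists side by side (SAP 6.1.1 and 6.1.2).**

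| Endpoint | p.17 SU discontinuation | p.35 AXI discontinuation | p.36 long-term follow-up | p.37 study discontinuation |
|---|---|---|---|---|
| OS, SU-AXI | not needed | yes | yes | yes |
| Second OS table | no | no | yes | yes |
| PFS, AXI (primary) | not needed | yes | **no** | yes |
| PFS, SU-AXI (primary) | not needed | yes | **no** | yes |
| PFS, first-line SU, prospective | yes | not relevant | **no** | yes |

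Page 17 is not needed in the SU-AXI rows, because those patients survived sunitinib. Page 37 is the only source common to all rows.

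**Step 2. Follow the rules for three patients, each without a page 37 death entry.**
- *Stops axitinib for intolerability with no assessment showing progression, dies within 3 months, death on page 36 only.* Neither page named in the PFS tables shows a death, so PFS status is 0, censored at axitinib discontinuation. In SU-AXI OS the same patient is dead.
- *Dies on sunitinib, death on page 17 only.* This is a first-line PFS event. In the second OS table the patient is censored at the latest visit date, and so has died for PFS but not for OS.
- *Dies on axitinib, death on page 35 only.* This is an event in SU-AXI OS and in both primary PFS endpoints, but is censored in the second OS table.

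**Step 3. Which analysis the second OS table serves.** Its position beside first-line sunitinib endpoints, its note on patients enrolled at axitinib start, and the first-line sunitinib OS analysis planned in SAP 8.2.2 (with no other visible derivation) all point to first-line sunitinib OS. If instead it covers only sunitinib followed by a non-axitinib second line, those patients survived sunitinib and never took axitinib, and pages 36 and 37 are sufficient.

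**Step 4. Direction.** When a death is replaced by censoring at or before its date, Kaplan-Meier passes that patient's weight to those still at risk. From the date of the lost death onwards, the curve is the same or higher. Between an earlier censoring date and the death it can be fractionally lower.

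**Step 5. Scale, illustration only.** The plan states no figure to reproduce, and the share of events lost, q, is not in the documents. Assume exponential times and a random share q of all events censored at the event time. The estimate then tends to S(t)^(1−q), and the median is multiplied by 1/(1−q). The 6.5-month investigator-assessed median (protocol 6 and 8.5) serves as reference. A simulation of 200,000 draws gave medians of 6.60, 6.83, 7.23 and 8.13 months.

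| q (assumed) | 6.5/(1−q), months | 0.5^(1−q) |
|---|---|---|
| 2% | 6.6 | 50.7% |
| 5% | 6.8 | 51.8% |
| 10% | 7.2 | 53.6% |
| 20% | 8.1 | 57.4% |

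Censoring before the death, as the PFS rule does, would make the shift somewhat smaller than shown.

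**Step 6. A ceiling for page 17.** Protocol 8.5 expects 68% of 525 sunitinib starters to reach a second line, leaving 525 × 0.32 = 168 who do not. Deaths that could sit only on page 17 lie within those 168; how many of them die on sunitinib is not stated.

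**The case against.** The strongest answer is page 37. It is in every list, carries a death box and a date, and the CRF asks for it whenever a patient leaves the study for any reason. If sites complete it for every death, no death is lost. This stands, and makes the risk conditional. It does not remove it, because the plan states no check that every death has a page 37.

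A reader might infer that the SU-AXI OS list, by adding pages 35 and 36, shows that the sponsor regards page 37 as incomplete. That does not follow: overlapping sources are ordinary redundancy, and SAP 6.2.3 gives page 37 priority for cause of death. But that priority covers cause only. TTF has a minimum-date rule for overlapping entries; OS and PFS have none.

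A reader might also take the PFS sentence as restricting death to pages 35 and 37. It says where death could be reported, not that nothing else counts, and the PFS time uses an unqualified date of death. A programmer could legitimately add page 36, but the text does not tell them to.

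Nor do the documents say that page 36 is where early off-treatment deaths are first reported. It is a six-monthly form, so a death within 3 months comes before its first scheduled completion and may well go to page 37. A PFS loss needs four things together: no documented progression, death inside the window, an entry on page 36, and none on page 37. Finally, the SAP lets data review meetings adapt PFS censoring, although deaths found only on page 36 are not among the cases it names.

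**Conclusion.** The inconsistency is real and visible in the SAP. Read literally, the PFS derivations miss a death recorded only on the long-term follow-up form, and the second OS table misses one recorded only on page 17 or 35. Either is censored, and survival is biased upward. The PFS part does not depend on any missing heading. The OS part rests on the second table serving first-line sunitinib OS, which is the most plausible reading but is not confirmed. The SU-AXI OS endpoint itself is not affected by the omission of pages.

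The size is unknown and may be zero. A reader might infer that deaths will certainly be lost, or put a number on them. The documents support neither: they give no rate of death on sunitinib and no rate of missing page 37 forms. The table of q values shows sensitivity only. For PFS, the four conditions that must coincide make its lower end more credible than its upper end.

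**What to change.** Add one paragraph to SAP 6.1 that defines a single death status and date per patient from CRF pages 17, 35, 36 and 37 and the adverse event form. Include a rule for conflicting dates and require this variable in every OS and PFS derivation. Apply the existing 3-month PFS criterion to that date. State in the heading of the second OS table which analysis it serves. List for the data review meetings any death without a page 37 entry and any death whose date differs between forms; the number of such cases then replaces the assumed q.

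The cost is a short SAP amendment. No new data are needed, and one shared variable is simpler to program than separate source lists.
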